1. PROTOCOL SUMMARY

1.1. Synopsis

Protocol Title: A Phase 1, Open-Label, Randomized, Crossover, Single Dose Study to Determine the Bioequivalence of 12.2 mg Tafamidis Free Acid Tablets and Commercial 20 mg Tafamidis Meglumine Capsules Administered Under Fasted Conditions and the Effect of Food on Oral Bioavailability of 12.2 mg Tafamidis Free Acid Tablets in Healthy Adult Participants

Brief Title: Phase 1 Study to Determine Bioequivalence of 12.2 mg Tafamidis Free acid Tablets and Commercial 20 mg Tafamidis Meglumine Capsules Administered Under Fasted Conditions and the Effect of Food on Oral Bioavailability in Healthy Adult Participants

Regulatory Agency Identification Number(s):

US IND Number:	CC1
EudraCT Number:	Not Applicable
ClinicalTrials.gov ID:	Not Available
Pediatric Investigational Plan Number:	Not Applicable
Protocol Number:	B3461103
Phase:	1

Rationale:

This study will be conducted to determine if a 12.2 mg tafamidis free acid tablet (Test) is bioequivalent to the commercial 20 mg tafamidis meglumine soft gelatin capsule (Reference) and to estimate the effect of food on the bioavailability of the 12.2 mg tafamidis free acid tablet.

Objectives and Endpoints:

Objectives	Endpoints
Primary: 
To establish the bioequivalence of 12.2 mg tafamidis free acid tablet (Test) and commercial 20 mg tafamidis meglumine soft gelatin capsules (Reference) in fasted healthy participants.	Primary: 
AUC_{inf} (if data permit, otherwise AUC_{last}) and C_{max} of tafamidis.
Secondary: 
To estimate the relative bioavailability of a single dose of the 12.2 mg tafamidis free acid tablet administered under fed conditions compared to a single dose of the 12.2 mg tafamidis free acid tablet administered under fasted conditions in healthy participants.	Secondary: 
Not Applicable
CC1 [REDACTED]	[REDACTED]
[REDACTED]	[REDACTED]

Overall Design:

This is a Phase 1, open-label, randomized, 3-way crossover, single dose study to determine the bioequivalence of PF-06291826 (tafamidis) 12.2 mg tafamidis free acid tablets versus commercial 20 mg tafamidis meglumine capsules administered under fasted conditions and to estimate the effect of food on the 12.2 mg tafamidis free acid tablet in healthy participants.

Number of Participants:

The sample size of 22 participants (11 participants per sequence in the fasted arms) to ensure a minimum of 18 PK evaluable participants for this 3-way crossover will provide 95% power that the 90% confidence interval for the ratio of Test to Reference for AUC_{inf} will lie within the acceptance region of (80%, 125%) and 89% power that 90% confidence interval for the ratio of Test to Reference treatment for C_{max} will lie within the acceptance region of (80%, 125%). Consequently, this study has approximately 85% power overall to demonstrate bioequivalence of the Test treatment to the Reference treatment [ie, equivalence in both AUC_{inf} and C_{max}]. This estimate is based on the assumption that the true ratio between Test and Reference treatments for both AUC_{inf} and C_{max} is 0.9.

The power calculations assumed the estimates of within participant standard deviations of 0.098 and 0.119 for $\log_e AUC_{inf}$ and $\log_e C_{max}$, respectively, obtained as an average from studies B3461030, B3461044 and B3461095.

Study Population:

Inclusion and exclusion criteria are listed below:

Inclusion Criteria

Participants must meet the following inclusion criteria to be eligible for enrollment into the study:

1. Participants aged 18 years or older (or the minimum age of consent in accordance with local regulations) at screening.
2. Healthy female participants of nonchildbearing potential and/or male participants who are overtly healthy as determined by medical evaluation including medical history, physical examination, and laboratory tests.
3. BMI of 17.5 to 30.5 kg/m²; and a total body weight >50 kg (110 lb).

Exclusion Criteria

Participants with any of the following characteristics/conditions will be excluded:

1. Evidence or history of clinically significant hematological, renal, endocrine, pulmonary, gastrointestinal, cardiovascular, hepatic, psychiatric, neurological, or allergic disease (including drug allergies, but excluding untreated, asymptomatic, seasonal allergies at the time of dosing).
 - Any condition possibly affecting drug absorption (eg, gastrectomy, cholecystectomy).
 - History of HIV infection, hepatitis B, or hepatitis C; positive testing for HIV, HBsAg, HBcAb, or HCVAb. Hepatitis B vaccination is allowed.
 - Hypersensitivity to any component of the formulations
2. Other medical or psychiatric condition including recent (within the past year) or active suicidal ideation/behavior or laboratory abnormality or other conditions or situations related to COVID-19 pandemic (eg, Contact with positive case, residence, or travel to an area with high incidence) that may increase the risk of study participation or, in the investigator's judgment, make the participant inappropriate for the study.

3. Use of prescription or nonprescription drugs, dietary and herbal supplements within 7 days or 5 half-lives (whichever is longer) prior to the first dose of study intervention. (Refer to Section 6.9 Prior and Concomitant Therapy for additional details).
4. Current use of any prohibited concomitant medication(s) or participant unwilling/unable to use a permitted concomitant medication(s). Refer to Section 6.9 Prior and Concomitant Therapy.
5. Previous administration with an investigational product (drug or vaccine) within 6 months (or as determined by the local requirement) or 5 half-lives preceding the first dose of study intervention used in this study (whichever is longer).
6. A positive urine drug test.
7. Screening seated BP ≥ 140 mm Hg (systolic) or ≥ 90 mm Hg (diastolic), following at least 5 minutes of seated rest. If BP is ≥ 140 mm Hg (systolic) or ≥ 90 mm Hg (diastolic), the BP should be repeated 2 more times and the average of the 3 BP values should be used to determine the participant's eligibility.
8. Standard 12-lead ECG that demonstrates clinically relevant abnormalities that may affect participant safety or interpretation of study results (eg, QTcF >450 ms, complete LBBB, signs of an acute or indeterminate- age myocardial infarction, ST-T interval changes suggestive of myocardial ischemia, second- or third- degree AV block, or serious bradyarrhythmias or tachyarrhythmias). If the uncorrected QT interval is >450 ms, this interval should be rate-corrected using the Fridericia method only and the resulting QTcF should be used for decision making and reporting. If QTcF exceeds 450 ms, or QRS exceeds 120 ms, the ECG should be repeated twice and the average of the 3 QTcF or QRS values used to determine the participant's eligibility. Computer-interpreted- ECGs should be overread by a physician experienced in reading ECGs before excluding a participant.
9. Participants with ANY of the following abnormalities in clinical laboratory tests at screening, as assessed by the study-specific laboratory and confirmed by a single repeat test, if deemed necessary:
 - AST or ALT level $\geq 1.5 \times$ ULN;
 - Total bilirubin level $\geq 1.5 \times$ ULN; participants with a history of Gilbert's syndrome may have direct bilirubin measured and would be eligible for this study provided the direct bilirubin level is \leq ULN.
10. History of alcohol abuse or binge drinking and/or any other illicit drug use or dependence within 6 months of Screening. Binge drinking is defined as a pattern of 5 (male) and 4 (female) or more alcoholic drinks in about 2 hours. As a general rule, alcohol intake should not exceed 14 units per week (1 unit = 8 ounces (240 mL) beer, 1 ounce (30 mL) of 40% spirit, or 3 ounces (90 mL) of wine).

Pfizer Confidential

11. Blood donation (excluding plasma donations) of approximately 1 pint (500 mL) or more within 60 days prior to dosing.
12. History of sensitivity to heparin or heparin-induced thrombocytopenia.
13. Unwilling or unable to comply with the criteria in the [Lifestyle Considerations](#) section of this protocol.
14. Investigator site staff directly involved in the conduct of the study and their family members, site staff otherwise supervised by the investigator, and sponsor and sponsor delegate employees directly involved in the conduct of the study and their family members.

Study Arms and Duration:

Eligible participants who continue to meet entry criteria will be admitted to the CRU on Day -1 and will be required to stay in the CRU for 8 overnight stays in each period. All participants will be discharged from the CRU following completion of the discharge evaluation, which includes adverse event monitoring, physical examination (at investigator discretion), vital signs, ECG measurements, and safety laboratory tests.

Study Intervention(s)			
Intervention Name	Tafamidis free acid tablet (fasted)	Tafamidis meglumine soft gelatin capsule (fasted)	Tafamidis free acid tablet (fed)
Arm Name (group of participants receiving a specific treatment or no treatment)	Treatment A	Treatment B	Treatment C
Unit Dose Strength(s)	12.2 mg	20 mg	12.2. mg
Route of Administration	Oral	Oral	Oral
Use	Experimental	Experimental	Experimental
IMP or NIMP/AxMP	IMP	IMP	IMP

Study Arm(s)			
Arm Title	Treatment A	Treatment B	Treatment C
Arm Type	Test - fasted	Reference – fasted	Test - fed
Arm Description	Participants will receive a single 12.2 mg tafamidis free acid tablet, fasted	Participants will receive a single commercial 20 mg tafamidis meglumine capsule	Participants will receive a single 12.2 mg tafamidis free acid tablet, fed

Statistical Methods:

Natural log-transformed AUC_{inf} , AUC_{last} , **CCI**, and C_{max} will be analyzed separately using a mixed effect model with sequence, period and treatment as fixed effects and participant within sequence as a random effect. Estimates of the adjusted mean differences (Test/Reference) and corresponding 90% confidence intervals will be obtained from the model. The adjusted mean differences and 90% confidence intervals for the differences will be exponentiated to provide estimates of the ratio of adjusted geometric means (Test/Reference) and 90% confidence intervals for the ratios. Treatment A (12.2 mg tafamidis free acid tablet fasted) will be the Test treatment, while Treatment B (commercial 20 mg tafamidis meglumine softgel capsule fasted) will be the Reference treatment.

Bioequivalence of between the 2 formulations will be concluded if the 90% confidence intervals for the ratio of adjusted geometric means for both AUC_{inf} (if data permit, otherwise AUC_{last}) and C_{max} fall wholly within the pre-specified criteria (80%, 125%).

For the food effect comparison, Treatment C (12.2 mg tafamidis free acid tablet, fed) will be the Test treatment, while Treatment A (12.2 mg tafamidis free acid tablet, fasted) will be the Reference treatment.

The PK parameters AUC_{inf} , C_{max} , AUC_{last} , **CCI** of tafamidis will be summarized descriptively by treatment. For AUC_{inf} , AUC_{last} , and C_{max} , individual participant parameters will be plotted against treatment. Concentrations will be listed and summarized descriptively by treatment and PK sampling time. Individual participant, mean and median profiles of the concentration-time data will be plotted by treatment. For summary statistics and median plots by sampling time, the nominal PK sampling time will be used. For individual participant plots by time, the actual PK sampling time will be used.

Ethical Considerations:

Participants will be expected to commit time and may experience some discomfort while undergoing study assessments. In addition, participants must avoid vaccination with live attenuated vaccines throughout the study. When relevant, it is recommended that participants keep their diet habits constant throughout the study.

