9.3.2 Statistical Methods for PK Data

For assessment of the bioequivalence objective of the study (Periods 1 and 2), natural log transformed AUC_{inf} , AUC_{last} , CCl and C_{max} will be analyzed separately using a mixed effect model with sequence, period and treatment as fixed effects and participant within sequence as a random effect. Estimates of the adjusted mean differences (Test-Reference) and corresponding 90% confidence intervals will be obtained from the model. The adjusted mean differences and 90% confidence intervals for the differences will be exponentiated to provide estimates of the ratio of adjusted geometric means (Test/Reference) and 90% confidence intervals for the ratios. Treatment A (12.2 mg tafamidis free acid tablet) will be the Test treatment, while Treatment B (commercial 20 mg tafamidis meglumine softgel capsule) will be the Reference treatment.

Bioequivalence of between the 2 formulations will be concluded if the 90% confidence intervals for the ratio of adjusted geometric means for both AUC_{inf} (if data permit, otherwise AUC_{last}) and C_{max} fall wholly within (80%, 125%).

For assessment of the food effect objective of the study (where treatment comparison occurs via fixed-sequence), natural log transformed AUC_{inf} , AUC_{last} , CC_{I} and C_{max} will be analyzed separately using a mixed effect model with treatment as fixed effects and participant as a random effect. Estimates of the adjusted mean differences (Test-Reference) and corresponding 90% confidence intervals will be obtained from the model. The adjusted mean differences and 90% confidence intervals for the differences will be exponentiated to provide estimates of the ratio of adjusted geometric means (Test/Reference) and 90% confidence intervals for the ratios. Treatment C (12.2 mg tafamidis free acid tablet, fed) will be the Test treatment, while Treatment A (12.2 mg tafamidis free acid tablet, fasted) will be the Reference treatment.

CCI

The plasma concentrations for tafamidis will be listed and summarized descriptively by nominal PK sampling time and treatment. Individual participant as well as mean and median profiles of the plasma concentration time data will be plotted by treatment using actual (for individual) and nominal (for mean and median) times respectively. Mean and median profiles will be presented on both linear and semi-log scales.

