9.5. Sample Size Determination

The sample size of 22 participants (11 participants per sequence in the fasted arms) to ensure a minimum of 18 PK evaluable participants for this 3-way crossover will provide 97% power that the 90% confidence interval for the ratio of Test to Reference for AUC_{inf} will lie within the acceptance region of (80%, 125%) and 89% power that 90% confidence interval for the ratio of Test to Reference treatment for C_{max} will lie within the acceptance region of (80%, 125%). Consequently, this study has approximately 86% power overall to demonstrate bioequivalence of the Test treatment to the Reference treatment [ie, equivalence in both AUC_{inf} and C_{max}]. This estimate is based on the assumption that the true ratio between Test and Reference treatments for both AUC_{inf} and C_{max} is 0.9.

The power calculations assumed the estimates of within participant standard deviations of 0.098 and 0.119 for $\log_e AUC_{inf}$ and $\log_e C_{max}$, respectively, obtained as an average from studies B3461030, B3461044 and B3461095.

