2.3. Study Design

This study will be a Phase 1, open label, randomized, 3-way crossover, single dose study to determine the bioequivalence of PF-06291826 (tafamidis) 12.2 mg tafamidis free acid tablets versus commercial 20 mg tafamidis meglumine capsules administered under fasted conditions and to estimate the effect of food on the 12.2 mg tafamidis free acid tablet in healthy participants.

A total of 22 participants will be enrolled to ensure a minimum of 18 completers. Participants withdrawn from the study may be replaced. Each period will be separated by a washout of at least 16 days between administration of study drug. Participants will be randomized to receive one of the treatment sequences shown in Table 2:

Table 2. B3461103 Treatment Sequence Schema

Sequence	Period 1	Period 2	Period 3
1 (n=11)	A	B	C
2 (n=11)	B	A	C

A: 12.2 mg tafamidis free acid tablet, fasted (Test)

B: Commercial 20 mg tafamidis meglumine soft gelatin capsule, fasted (Reference)

C: 12.2 mg tafamidis free acid tablet, fed (Test)

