Appendix 1. SAS Code for Analyses

An example of the PROC MIXED code is provided below:

For primary objective: Treatment A (Test) vs Treatment B (Reference)

```
proc mixed data=tab.pk;
  where trt in ("A", "B");
    class seq period trt participant;
    model l&var=seq period trt/ ddfm=KR;
    random participant(seq) /participant=participant(seq);
    lsmeans trt;
    estimate 'A vs B' trt 1 -1 /cl alpha=0.1;

    ods 'Estimates' out=est&var;
    ods 'lsmeans' out=ls&var;
    ods 'covparms' out=cov&var;
    ods 'tests3' out=tst&var;
run;

/* Letter assignments for treatments (trt) within the estimate statement above are as follows
A: 12.2 mg tafamidis free acid tablet, fasted (Test)
B: Commercial 20 mg tafamidis meglumine soft gelatin capsule, fasted (Reference) */
```

For secondary objective: Treatment C (Test) vs Treatment A (Reference)

```
proc mixed data=tab.pk;
  where trt in ("A", "C");
    class trt participant;
    model l&var=trt / ddfm=KR;
    random participant / subject=participant;
    lsmeans trt;
    estimate 'C vs A' trt -1 1 /cl alpha=0.1;

    ods 'Estimates' out=est&var;
    ods 'lsmeans' out=ls&var;
    ods 'covparms' out=cov&var;
    ods 'tests3' out=tst&var;
run;

/* Letter assignments for treatments (trt) within the estimate statement above are as follows;
A: 12.2 mg tafamidis free acid tablet, fasted (Reference)
C: 12.2 mg tafamidis free acid tablet, fed (Test) */
```

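### The protocol synopsis and Section 9.5 report different power from the same inputs (AUCinf 95% against 97%, overall about 85% against about 86%), and neither AUCinf figure is the rounded exact value under the planned analysis

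*Protocol*

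**What the plan says.** Protocol Section 1.1 (Synopsis, Number of Participants) states for AUCinf that "this 3-way crossover will provide 95% power that the 90% confidence interval for the ratio of Test to Reference" lies within the limits. It gives 89% for Cmax and concludes: "Consequently, this study has approximately 85% power overall to demonstrate bioequivalence".

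Protocol Section 9.5 (Sample Size Determination) states for the same comparison that "this 3-way crossover will provide 97% power that the 90% confidence interval for the ratio of Test to Reference" lies within the limits. It gives the same 89% for Cmax and concludes: "Consequently, this study has approximately 86% power overall to demonstrate bioequivalence".

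The inputs do not differ between the two. Both give 22 participants, 11 per sequence, to secure 18 evaluable for PK. Both take a true ratio of 0.9 for each endpoint and limits of 80% to 125%. Both cite the same three earlier studies as the source of variability: "The power calculations assumed the estimates of within participant standard deviations of 0.098 and 0.119" for log AUCinf and log Cmax.

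The SAP repeats the numbers of participants (SAP Section 2.3: "A total of 22 participants will be enrolled to ensure a minimum of 18 completers") but states no power. SAP Section 2.1 records no departure from the protocol's analysis plan.

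**The concern.** One set of inputs cannot give two different powers for AUCinf. Power is the quantitative justification for the sample size, and the primary objective requires both endpoints to pass. A reader of the synopsis and a reader of Section 9.5 get different justifications, and nothing in the documents says which is intended.

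A single mistyped digit is an unlikely cause, because the overall figure moves in step with the AUCinf figure. That pattern points to two calculations, or two versions of one, that were never reconciled.

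**Working it through.** **Step 1. The plan's overall figures.** Each is the product of its own two components:

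- Synopsis: 0.95 × 0.89 = 0.8455, printed as about 85%.
- Section 9.5: 0.97 × 0.89 = 0.8633, printed as about 86%.

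Cmax is 89% in both, so the disagreement lies entirely in AUCinf.

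**Step 2. Inputs for a recalculation.**

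- Limits ln 0.8 = −0.22314 and ln 1.25 = 0.22314; true difference ln 0.9 = −0.10536 (Section 9.5).
- One-sided 5% for each of two tests, that is, a 90% interval (Protocol Section 9.1).
- SDs 0.098 and 0.119; 18 evaluable, taken as 9 per sequence.
- Model: Protocol Section 9.3.2 (Statistical Methods for PK Data) and SAP Section 6.1 confine the formulation comparison to Periods 1 and 2. SAP Appendix 1 fits "model l&var=seq period trt/ ddfm=KR" to treatments A and B only. That is a 2×2 crossover with n − 2 = 16 df; t(0.95, 16) = 1.7459.

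**Step 3. Standard errors.** SE = SD × √((1/n1 + 1/n2)/2). At 9/9 the factor is √(1/9) = 1/3.

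- AUCinf: 0.098/3 = 0.03267. Distance to the lower limit: 0.11778/0.03267 = 3.606 SE.
- Cmax: 0.119/3 = 0.03967. Distance to the lower limit: 0.11778/0.03967 = 2.969 SE.

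**Step 4. Power.** The documents name no power method, so three were tried. Exact power integrates over the distribution of the estimated SD; the noncentral t form gives the same values.

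| Case (printed SDs) | AUCinf | Cmax | Product |
|---|---|---|---|
| Exact, 9/9, df 16 | 96.43% | 88.40% | 85.24% |
| Shifted central t, 9/9, df 16 | 95.93% | 88.06% | 84.47% |
| Normal approximation, 9/9 | 97.50% | 90.73% | 88.47% |
| Exact, 9/9, df 17 (no sequence term) | 96.50% | 88.55% | 85.46% |
| Exact, 9/9, df 32 | 97.01% | 89.63% | 86.95% |
| Exact, 7/11, df 16 | 95.70% | 86.96% | 83.22% |
| Exact, 8/9 (17 evaluable), df 15 | 95.44% | 86.48% | 82.54% |
| Exact, 11/11 (all 22), df 20 | 98.62% | 93.62% | 92.33% |

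Under the planned model, AUCinf power rounds to 96%: 1.4 points above the synopsis and 0.6 points below Section 9.5. Cmax rounds to 88%, not 89%.

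**Step 5. Could rounding of the SDs explain it?** At 9/9, df 16, exact, over every SD that prints as 0.098 or 0.119:

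- AUCinf runs from 96.29% to 96.56%, Cmax from 88.17% to 88.63%, and the product from 84.90% to 85.59%.
- Printing 97% needs an AUCinf SD of at most about 0.0977. Printing 89% needs a Cmax SD just under 0.1188.
- If overall power is the product of unrounded components, printing 86% needs SDs near 0.0975 and 0.1185 (85.59%). If the printed components are multiplied, the looser pair is enough.
- An AUCinf figure that prints as 95% needs an SD of about 0.1012 or more, which cannot print as 0.098.

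**Step 6. Could any plausible setting give 95% and 89% together?** A search covered the three methods, 16 to 22 evaluable, 5 to 11 per sequence, df of n − 2, n − 1 and 2n − 4, and the rounding range of both SDs. Wherever Cmax can print as 89%, AUCinf is at least 96.27%. AUCinf alone can come down to 95% at 18 evaluable (shifted central t with a 7/11 split: 95.05% to 95.36%), but Cmax is then 86.4% to 86.9%. The pair 95/89 never occurs; 97/89 occurs in several settings.

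**Step 7. Dependence between endpoints.** The product assumes independence. At the printed SDs, overall power at 18 evaluable must lie between 96.43 + 88.40 − 100 = 84.83% and 88.40%, whatever the correlation.

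**The case against.** The strongest counter-argument is that 16 df is inferred from the analysis model and not stated with the power calculation. Both power statements describe a 3-way crossover, and the synopsis's account of the model does not restrict the comparison to Periods 1 and 2. With 17 df the exact AUCinf power at the printed SD is 96.501%, which prints as 97%, and Cmax is 88.55%, which prints as 89%. A three-period fit would have about 33 residual df (54 − 18 − 2 − 1); with an 8/10 split it gives 96.9% and 89.3%. Section 9.5 may therefore be correct as the sponsor calculated it, with no rounding of the SDs. On this view the likely defect is one stale synopsis figure, and the consequence is negligible because each AUCinf figure is within 2 points of the exact value.

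Part of this stands. The statement that neither AUCinf figure is the rounded value depends on 16 df, and the evidence does favour Section 9.5 over the synopsis. But 17 df drops the sequence term that the protocol and SAP both plan. A three-period fit is not the planned formulation comparison, and at 9/9 with 32 df it prints 97/90, not 97/89. None of these routes rescues the synopsis pair, and none removes the contradiction between the two sections. The small size limits the importance of the point, not its truth.

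**Conclusion.** The concern holds. From identical stated inputs the protocol reports AUCinf power of 95% and 97%, and overall power of about 85% and about 86%, so at least one set is wrong. This conclusion needs no modelling.

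Under the planned analysis, with 9 evaluable per sequence, 16 df and the printed SDs, the exact figures are about 96% for AUCinf, 88% for Cmax and 85% for the product. The 95/89 pair in the synopsis does not follow from the inputs under any setting tried. The 97/89 pair in Section 9.5 can follow from unrounded SDs slightly below those printed, or from degrees of freedom other than those of the planned model.

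The effect is editorial. Every figure is above 80%, and sample size, design, analysis and decision rule stay as they are. The numerical part rests on the 16 df reading and on a power method that the documents do not name; the overall figure also rests on independence of the two endpoints.

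**What to change.** Rerun the power calculation once at 18 evaluable with the unrounded SDs from the three source studies, and print the same three figures in the Synopsis and in Section 9.5. If the rerun confirms 97/89/86, correct the synopsis. If the printed SDs are exact and the planned 16 df model is used, both places should read about 96/88/85. State the evaluable number, degrees of freedom and method beside the figures, and say that overall power is a product under independence if that is how it was obtained.

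The cost is one short calculation and a few digits in one or both sections.
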